Background and rationale	
The advent of simple direct-acting antiviral hepatitis C (HCV) therapies with cure rates >95% is one of the greatest medical advances in decades, having led to a reversal in liver-related mortality. In Australia, treatment uptake has declined between 2016 (32,000 treated) and 2019/20 (2019: 11,500; 2020: 8,500).¹ Progress towards HCV elimination has been impeded by COVID-19, affecting the delivery of national and state-based HCV strategies. Improving HCV treatment uptake to reduce disease burden is a key aim of global, national and state-based HCV strategies.²⁻⁴
 
Scale-up of HCV testing and treatment will be required to achieve elimination by 2030. Increasing HCV testing is hampered by diagnostic pathways requiring multiple visits and loss to follow-up, amplified in key populations, such as people who inject drugs. In Australia, 81% of people have had HCV antibody testing (indicates exposure), but only 47% have been HCV RNA tested (indicates active infection and the need for HCV treatment).⁵ Mathematical modelling suggests that HCV RNA testing needs to increase by at least 50% annually to achieve elimination in Australia by 2030.⁶
 
The approval of the Xpert® HCV Viral Load Fingerstick test for detection of active HCV infection in one hour at the point-of-care by the Therapeutic Goods Administration is a ‘game-changer’. This HCV point-of-care test enables diagnosis and treatment in a single-visit, increases testing acceptability, and reduces loss to follow-up, addressing the drop-off in the HCV care cascade.
 
The Kirby Institute is an international leader in research evaluating the Xpert HCV assay (Grebely Lancet Gastro Hep 2017), having built a large network of Xpert platforms for HCV testing in needle and syringe programs, prisons, drug treatment clinics, tertiary hospitals,

	
and Aboriginal Community Controlled Health Service. In Kirby-led research, point-of-care HCV testing interventions in needle and syringe programs and prisons have resulted in high HCV treatment uptake (70-90%).
 
The Kirby Institute and Flinders University will establish the Australian National HCV Point-of-care Testing Program for the scale-up of point-of-care HCV RNA testing in services with high prevalence of HCV infection, including community health centres, drug treatment clinics, needle and syringe programs, and prisons. This program will include the development of standard operating procedures, logistics/deployment, initial set-up, an operator training program, and quality assurance and competency assessment program.
 
In settings with lower HCV antibody prevalence, immediate point-of-care HCV RNA testing may not be cost-effective (\$60/test), and a screening strategy using a point-of-care HCV antibody test (approximately \$10/test) followed by a HCV RNA test in people who are HCV antibody positive may be more cost-effective and time efficient. However, although there are HCV antibody tests available for use in Australia, there are none currently approved by the Therapeutics Goods Administration. It is critical to evaluate the cost and time effectiveness of different testing strategies to optimise testing and government funding and to inform clinical utility. Understanding and addressing implementation challenges is critical to rapidly translate HCV point-of-care testing into practice and policy.
 
This protocol describes an observational cohort study that will be established to evaluate initial point-of-care antibody testing before reflex HCV RNA testing. There are currently no TGA approved HCV antibody tests, so testing can only be evaluated within a research study with appropriate informed consent. An evaluation of the HCV treatment uptake following scale-up of point-of-care HCV antibody testing followed by HCV RNA testing is therefore needed.

Study objectives
	
Primary Objective
 
To evaluate the proportion of HCV infected (HCV RNA quantifiable) participants who initiate HCV treatment at 12 weeks following HCV RNA testing.

	
Secondary Objectives
 
 1. To evaluate the proportion of people who accept point-of-care testing among those offered testing. 2. To evaluate the prevalence of current HCV infection (HCV RNA quantifiable) among people tested. 3. To evaluate the HCV antibody prevalence among people tested. 4. To evaluate the time to treatment uptake among people receiving point-of-care HCV antibody testing with reflex HCV RNA testing in those who are HCV antibody detectable who received HCV treatment; 5. To evaluate the proportion of HCV RNA positive participants who initiate HCV treatment at 12 months (52 weeks) following HCV RNA testing. 6. To evaluate the proportion of participants who complete HCV direct-acting antiviral (DAA) treatment following point-of-care HCV antibody testing with reflex HCV RNA testing in those who are HCV antibody detectable who received HCV treatment; 7. To evaluate the proportion of participants who achieve an SVR (defined as HCV RNA below the lower limit of quantitation at post treatment week 12) following point-of-care HCV antibody testing with reflex HCV RNA testing in those who are HCV antibody detectable who received HCV treatment. 8. To evaluate the proportion of participants who are HCV RNA negative at 12 months (52 weeks) following HCV RNA testing. 9. To evaluate the cost-effectiveness of this testing strategy.

Participant population
	
Participants will be included from settings that provide services to people with a risk factor for the acquisition of HCV infection, including drug treatment clinics, needle and syringe programs, prisons, mobile outreach services, community health services, mental health services, homelessness services, and other appropriate settings nationally. It is anticipated that approximately 40,000 participants will be screened for HCV infection using point-of-care HCV testing.
 
Inclusion criteria

	
Participants are eligible for inclusion if the following criteria are met:
 
 a. Provide informed consent b. ≥ 18 years of age. 
Exclusion criteria
 
 a. Is unable or unwilling to provide informed consent
Study design	
This is an observational cohort study. Participants will attend a single visit where they will provide informed consent and receive point-of-care HCV testing. All other study procedures will comprise data collection only.

Treatment of participants	
No treatment will be prescribed as a part of this study. Participants who are HCV RNA detectable will be linked to standard of care for any other clinical assessments and treatment initiation.

Study procedures	
All participants receiving HCV testing at sites participating in this study, and who meet the study criteria will be identified and offered participation in the study. Participants will undergo verbal or written informed consent followed by HCV point-of-care testing. As this is an observational cohort study, further study procedures will comprise data collection only.
 
For participants who have previously been told they have HCV infection, or for people who have previously received HCV treatment, testing will be performed using point-of-care HCV RNA testing via Xpert HCV Viral Load Fingerstick assay using the GeneXpert machine (results in one hour).
 
For all other participants who have not previously been told they have HCV infection nor have previously received HCV treatment, testing will be performed using point-of-care HCV antibody testing. If the result is HCV antibody positive, individuals will undergo reflex HCV RNA testing.
 
Participants will not receive treatment as a part of this study. Participants who are HCV RNA positive will be linked to standard of care for any other clinical assessments and treatment initiation.


Statistics
	
Primary outcome
 
The proportion of HCV RNA detectable participants who initiate HCV treatment within 12 weeks of HCV RNA testing.
 
Sample size
 
Overall, 40,000 point-of-care HCV tests will be performed in different settings as part of the Australian National HCV Point-of-care Testing Program. It is estimated that the HCV prevalence will be 15% (n=6,000 people who are HCV RNA detectable) and the treatment uptake following testing will be 65% (n=3,900). Under these assumptions, the 95% confidence intervals around the estimate for HCV treatment uptake will be 64.0%-66.0% and for HCV RNA prevalence will be 14.7%-15.4%. For analyses evaluating factors associated with HCV treatment uptake, we will have 90% power to detect an odds ratio of 1.20 or greater ($\alpha=0.05$) for a variable that is 50% prevalent (i.e. recent injecting drug use).
 
Analysis will follow the STROBE guidelines for observational studies. The analysis of the primary outcome will occur when all patients have completed 12 weeks of follow-up (from enrolment) or have been permanently lost to follow-up. Participant flow will be summarised, showing the numbers of participants included.

--------------------------	--

1. Background and rationale

In Australia, hepatitis C virus (HCV)-related morbidity and mortality have doubled in the past decade, with health care costs of \$220 million per annum.¹ In 2019, 128,000 Australians were living with HCV infection.² The majority of new (90%) and existing (80%) cases of HCV infection in Australia occur among people who inject drugs (PWID).^{1,2}

The advent of simple direct-acting antiviral (DAA) HCV therapies with cure rates >95% is one of the greatest medical advances in decades, having led to a reversal in liver-related mortality.¹¹ In Australia, treatment uptake has declined between 2016 (32,000 treated) and 2019/20 (2019: 11,500; 2020: 8,500).¹ Progress towards HCV elimination has been impeded by COVID-19, affecting the delivery of national and state-based HCV strategies. Improving HCV treatment uptake to reduce disease burden is a key aim of global, national and state-based HCV strategies.²⁻⁴

Globally, HCV testing and diagnosis remains low.⁴ Testing pathways involve an HCV antibody test to confirm exposure and an HCV RNA test to detect active infection. This two-step pathway requires up to 5 visits to practitioners and off-site phlebotomists, leading to a drop-off in the diagnosis of active infection.² In Australia, 81% of people have had HCV antibody testing (indicates exposure), but only 47% have been HCV RNA tested (indicates active infection and the need for HCV treatment).⁵ Mathematical modelling suggests that HCV RNA testing needs to increase by at least 50% annually to achieve elimination in Australia by 2030.⁶

Point-of-care HCV testing increases linkage to care.⁷ Our group led the first evaluation of a point-of-care HCV RNA assay^{8,9}, the Xpert HCV Viral Load Fingerstick point-of-care test, enabling same-day diagnosis of active infection in one hour (sensitivity and specificity, 100%) at the point-of-care, enabling diagnosis and treatment in a single visit, improving treatment uptake.⁹ This research facilitated the recent approval of the assay by the Therapeutics Good Administration (TGA), providing an unprecedented opportunity to scale-up HCV testing and treatment. Scale-up of HCV testing will be most impactful in settings with high HCV prevalence (e.g. those providing care for people who inject drugs), including prisons, drug treatment clinics, and needle and syringe programs. Point-of-care HCV RNA testing can also be combined with outreach models and mobile clinics to provide access to testing and treatment to those who may not have been tested or treated to date. The next step is to translate this novel discovery into routine clinical practice to scale-up testing and treatment to facilitate HCV elimination.

The Kirby Institute is an international leader in research evaluating the Xpert HCV assay, having built a large network of Xpert platforms for HCV testing in needle and syringe programs, prisons, drug treatment clinics, tertiary hospitals, and Aboriginal Community Controlled Health Services. In Kirby-led research, point-of-care HCV testing interventions in needle and syringe programs and prisons have resulted in high HCV treatment uptake (75-90%). The Kirby Institute and Flinders

University also have a strong track record of implementing point-of-care testing for STIs and COVID-19, providing an ideal foundation to scale-up point-of-care HCV testing in Australia.

The Kirby Institute and Flinders University will establish the Australian National HCV Point-of-care Testing Program for the scale-up of point-of-care HCV testing in services caring for people with risk factors for the acquisition of HCV infection (e.g. drug treatment clinics, needle and syringe programs, prisons, mobile outreach services, community health services, mental health services, and homelessness services).

In settings with lower HCV antibody prevalence, immediate point-of-care HCV RNA testing may not be cost-effective (\$60/test), and a screening strategy using a point-of-care HCV antibody test (approximately \$10/test) followed by a HCV RNA test in people who are HCV antibody positive may be more acceptable to clients and service providers given a quicker turnaround time for an HCV antibody detectable result. However, although there are HCV antibody tests available for use in Australia, there are none currently approved by the Therapeutics Goods Administration. Therefore, testing can only be evaluated within a research study with appropriate informed consent. It is critical to evaluate the cost and time effectiveness of different testing strategies to optimise testing and government funding and to inform clinical utility.

This protocol describes an observational cohort study that will be established to evaluate HCV treatment uptake following scale-up of point-of-care HCV antibody testing followed by HCV RNA testing. This information will provide critical information on the effectiveness of this testing strategy to enhance HCV treatment.

2. Hypotheses

Primary Hypothesis

An intervention integrating HCV RNA testing (predominantly through point-of-care testing) will lead to a high uptake of HCV treatment (>65%) among people at increased risk for HCV infection.

3. Study objectives

Primary Objective

To evaluate the proportion of HCV infected (HCV RNA quantifiable) participants who initiate HCV treatment at 12 weeks following HCV RNA testing.

Secondary Objectives

1. To evaluate the proportion of people who accept point-of-care testing among those offered testing.
2. To evaluate the prevalence of current HCV infection (HCV RNA quantifiable) among people tested.

3. To evaluate the HCV antibody prevalence among people tested.
4. To evaluate the time to treatment uptake among people receiving point-of-care HCV antibody testing with reflex HCV RNA testing in those who are HCV antibody detectable who received HCV treatment;
5. To evaluate the proportion of HCV RNA positive participants who initiate HCV treatment at 12 months (52 weeks) following HCV RNA testing.
6. To evaluate the proportion of participants who complete HCV direct-acting antiviral (DAA) treatment following point-of-care HCV antibody testing with reflex HCV RNA testing in those who are HCV antibody detectable who received HCV treatment;
7. To evaluate the proportion of participants who achieve an SVR (defined as HCV RNA below the lower limit of quantitation at post treatment week 12) following point-of-care HCV antibody testing with reflex HCV RNA testing in those who are HCV antibody detectable who received HCV treatment.
8. To evaluate the proportion of participants who are HCV RNA negative at 12 months (52 weeks) following HCV RNA testing.
9. To evaluate the cost-effectiveness of this testing strategy.

4. Participant population

Participants will be included from settings that provide services to people with a risk factor for the acquisition of HCV infection, including drug treatment clinics, needle and syringe programs, prisons, mobile outreach services, community health services, mental health services, homelessness services, and other appropriate settings nationally. It is anticipated approximately 40,000 participants will be screened for HCV infection using point-of-care HCV testing.

Inclusion criteria

Participants are eligible for inclusion if the following criteria are met:

- a. Provide informed consent
- b. ≥ 18 years of age.

Exclusion criteria

- b. Is unable or unwilling to provide informed consent

5. Study design

This is an observational cohort study. Participants will attend a single visit where they will provide informed consent and receive point-of-care HCV testing. All other study procedures will comprise data collection only.

Participants will be offered treatment as standard of care. Participants who are HCV RNA detectable will also be linked to standard of care for any other clinical assessments and treatment

initiation, and local health staff may provide counselling and medical advice for these tests, and link participants with support services available in their state or territory.

Participants who return to the same site at a later date and require further HCV testing (as standard practice or due to a risk factor) can do so through the study without having to consent and enrol again. There is no time restrictions for when participants can receive another test, this is dependent on the individual case.

6. Treatment of participants

No treatment will be prescribed as a part of this study.

7. Study procedures

7.1 Visits and Procedures

All participants receiving HCV testing at the participating sites will be identified. Site staff will discuss the research study with participants, and written or verbal consent will be obtained. If written consent, the participant will date and sign the participant information sheet and consent form together with the date and signature of the person conducting the consent discussion. If verbal consent is utilised the person conducting the consent will sign the verbal consent form to confirm that the study has been explained to the participant and consent has been given. A copy of the signed participant information and consent form will then be offered to the participant. Participants will then undergo HCV point-of-care testing. Further study procedures will comprise data collection at Week 12 and Week 52 only.

For participants who have previously been told they have HCV infection, or for people who have previously received HCV treatment, testing will be performed using point-of-care HCV RNA testing via Xpert HCV Viral Load Fingerstick assay using the GeneXpert machine (results in one hour). For all other participants who have not previously been told they have HCV infection nor have previously received HCV treatment, testing will be performed using point-of-care HCV antibody testing (results within 20 minutes). If the result is HCV antibody positive, individuals will undergo reflex HCV RNA testing. Where possible, the HCV RNA test will be performed via Xpert HCV Viral Load Fingerstick assay using the GeneXpert machine. If not available, HCV RNA testing will be performed via other standard of care methods.

The following participant information will be collected as part of this study, from the participating sites existing medical records available at the site, by site staff:

- Name code
- Aboriginal and Torres Strait Islander status
- Gender
- Age
- Medical Record Number
- HCV testing and status

Additional data collection for HCV RNA positive patients only:

- Previous HCV treatment
- HIV testing and status
- HBV testing and status
- HCV treatment regimen prescribed
- HCV treatment proposed duration
- HCV treatment start and end date
- Treatment completion (including reasons for not completing treatment)
- Treatment outcome (including reasons for not responding to treatment)

Additionally, a record of the overall number of patients who declined an HCV RNA test will be obtained from sites that record this data.

Assessment / Procedure	HCV Testing	Data Review* (Week 12)	Data Review* (Week 52)
Provide informed consent	X		
Basic demographics	X		
Finger-stick point-of-care HCV testing	X		
Treatment uptake		X	X
Treatment outcome		X	X
HCV RNA status			X
HIV/HBV testing and status			X

*Data review of medical records for patients who are HCV RNA detectable only

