8.2 Sample size

Overall, 40,000 point-of-care HCV tests will be performed in different settings as part of the Australian National HCV Point-of-care Testing Program. It is estimated that the HCV prevalence will be 15% (n=6,000 people who are HCV RNA detectable) and the treatment uptake following testing will be 65% (n=3,900). Under these assumptions, the 95% confidence intervals around the estimate for HCV treatment uptake will be 64.0%-66.0% and for HCV RNA prevalence will be 14.7%-15.4%. For analyses evaluating factors associated with HCV treatment uptake, we will have 90% power to detect an odds ratio of 1.20 or greater ($\alpha=0.05$) for a variable that is 50% prevalent (i.e. recent injecting drug use).

Analysis will follow the STROBE guidelines for observational studies. The analysis of the primary outcome will occur when all patients have completed 12 weeks of follow-up (from enrolment) or have been permanently lost to follow-up. Participant flow will be summarised, showing the numbers of participants included. The primary endpoint will be the proportion of participants who initiate HCV treatment within 12 weeks of HCV RNA testing. The secondary endpoints will be:

- Proportion of people who accept point-of-care testing among those offered testing.
- Proportion of people who are HCV RNA detectable among people tested.
- Time to HCV treatment uptake following finger-stick point-of-care HCV antibody testing with reflex HCV RNA testing among people who receive treatment.
- Proportion of HCV RNA detectable participants who initiate HCV DAA treatment at 12 months (52 weeks) following enrolment.
- Proportion of participants who complete HCV direct-acting antiviral (DAA) treatment.
- Proportion of participants who achieve an SVR (defined as HCV RNA below the lower limit of quantitation at post treatment week 12).
- To evaluate the proportion of HCV RNA detectable participants who are HCV RNA negative at 12 months (52 weeks) following finger-stick point-of-care HCV antibody testing with reflex HCV RNA testing.
- Cost-effectiveness of different testing strategies.

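### The only refusal count listed is for HCV RNA tests, so the endpoint on acceptance of point-of-care testing cannot be estimated for people offered the antibody test first

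*Protocol*

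**What the plan says.** Secondary objective 1 (Protocol synopsis and Section 3) is "To evaluate the proportion of people who accept point-of-care testing among those offered testing". Section 8.2 repeats it as a secondary endpoint: "Proportion of people who accept point-of-care testing among those offered testing". Neither wording is limited to RNA testing.

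The synopsis and Section 7.1 set two routes. People previously told they have HCV, or previously treated, go straight to the point-of-care RNA test. The other route is introduced by "For all other participants who have not previously been told they have HCV infection nor have previously received HCV treatment, testing will be performed", and the test it names is the point-of-care antibody test. RNA testing follows on that route only after a positive antibody result.

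On refusals, Section 7.1 lists one item: "a record of the overall number of patients who declined an HCV RNA test will be obtained from sites that record this data".

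**The concern.** An acceptance proportion needs everyone who was offered a test, including those who said no. In the antibody-first group, a person who refuses at the first offer has refused an antibody test. Such a person never reaches the point at which an RNA test could be declined. As written, this group supplies acceptors but no first-offer decliners.

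The group matters to the study's own rationale. Section 1 gives possible greater acceptability to clients and service providers as a reason for screening with the antibody test. The acceptance endpoint is where that would be examined, and no listed item records refusals of that test.

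The timing matters too. Section 8.2 leaves the detailed analysis plan until near the end of the study. A plan written then can choose how to use the counts that exist, but it cannot recover refusals that were never logged.

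**Working it through.** **Step 1. Could another listed source supply the missing refusals?**

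- Section 7.1 begins from people who are tested: "All participants receiving HCV testing at the participating sites will be identified". Those who decline are outside that group.
- Section 4 excludes people unwilling to consent.
- The schedule in Section 7.1 has a row "Finger-stick point-of-care HCV testing" but no row for offers or refusals.
- Section 7.2 completes case report forms for each participant, so non-participants have none.
- Section 7.3 describes a database of GeneXpert test results, not of offers.

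None of these captures a refused antibody test.

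**Step 2. What does the single count contain?** Read literally, it holds two kinds of event: refusal of a direct RNA test, which is a first-offer refusal, and refusal of reflex RNA testing by someone who has already accepted a point-of-care antibody test. The second is not a refusal of the first offer. Section 7.1 also allows RNA testing by standard-of-care methods where GeneXpert is unavailable, so what is refused at that stage need not be a point-of-care test.

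**Step 3. Direction of error if all acceptors are set against this count.** The protocol states no acceptance figure to reproduce, so all inputs here are symbols or assumptions.

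- p = share of first offers that are antibody-first
- aA, aR = true acceptance of a first-offered antibody or RNA test
- s = antibody positivity among those tested; r = refusal of reflex RNA testing

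True acceptance: A = p·aA + (1−p)·aR.

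Apparent acceptance = A / [A + (1−p)(1−aR) + p·aA·s·r].

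The true denominator is A + (1−p)(1−aR) + p(1−aA) = 1. The apparent figure is therefore too high when p·aA·s·r < p(1−aA), that is, when **s·r < (1−aA)/aA**.

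- aA = 0.80: limit 0.20/0.80 = 0.25
- aA = 0.95: limit 0.05/0.95 = 0.053

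**Step 4. Illustration, with reflex refusals set to zero (s·r = 0).** With aA = aR = 0.80:

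| p | Apparent acceptance |
|---|---|
| 0.3 | 0.80/0.94 = 85.1% |
| 0.5 | 0.80/0.90 = 88.9% |
| 0.7 | 0.80/0.86 = 93.0% |

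With p = 0.5, overall acceptance still 80%, but acceptance differing by route:

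- aA = 0.90, aR = 0.70: 0.80/0.95 = 84.2%
- aA = 0.70, aR = 0.90: 0.80/0.85 = 94.1%

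**Step 5. Effect of reflex refusals.** At p = 0.5, aA = aR = 0.80 and s·r = 0.25, the reflex term is 0.5 × 0.80 × 0.25 = 0.10. The apparent figure is then 0.80/(0.80 + 0.10 + 0.10) = 80%: the two errors cancel. Above that limit the apparent figure is too low.

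**The case against.** The strongest reply is that HCV RNA test is loose wording for any HCV test offered. The protocol does use the terms loosely: the synopsis speaks of scaling up point-of-care RNA testing where Section 1 drops RNA, and the primary hypothesis describes the whole strategy as an intervention integrating RNA testing. An overall number of decliners also fits a single site tally. This stands as a real possibility. Against it, Section 7.1 itself separates the two tests. Even on the generous reading, sites that take the wording differently would return counts that cannot be pooled, so the item still needs correcting.

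A second reply is that no analysis is prescribed that sets all acceptors against RNA refusals only, and that a later plan could match numerator to denominator. That is fair as to the inflated percentage. It does not fill the gap: the endpoint would then cover RNA-first offers only, and even that needs direct refusals to be separable from reflex ones.

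Three stronger readings may tempt a reader, and the documents do not support them.

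- *The bias is always upward.* It is upward only under the condition in Step 3. The limit is demanding at 80% antibody acceptance but small at 95%.
- *Several thousand refusals will be lost.* Scaling to 40,000 would assume that every site records refusals and that 40,000 is a number of first offers. Section 7.1 limits the count to sites that record it, Section 8.2 speaks of tests, and Section 5 allows repeat testing without new enrolment.
- *Reflex refusals can be read off the participant item "HCV testing and status".* That item can show that an RNA result is missing, but not why. An invalid or error result, or the person leaving, would look the same as a refusal.

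On weight, this is a descriptive secondary endpoint with no target or sample size of its own, and it was always going to be partial across sites. That limits its importance.

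**Conclusion.** The concern holds in this form: as written, the listed data do not allow the acceptance endpoint to be estimated for the antibody-first group, and the one refusal count combines two different events. If that count is nevertheless set against all acceptors, acceptance is overstated when antibody positivity times reflex refusal is below (1−aA)/aA. That is probably the likelier direction, but the documents do not establish it. The size cannot be estimated from them either; the percentages above rest wholly on assumed acceptance rates and routing shares.

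Confidence is moderate, because the conclusion depends on taking HCV RNA test literally. The matter should be corrected while refusals can still be logged. It does not touch the primary outcome, which concerns treatment initiation among people with detectable HCV RNA.

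**What to change.** Replace the refusal item in Section 7.1 with three separate counts, at sites that record refusals: patients who declined (a) the first-offered point-of-care antibody test, (b) the first-offered point-of-care RNA test, and (c) reflex RNA testing. Compute acceptance from (a) and (b), with acceptors and decliners both limited to those recording sites. Report (c) on its own.

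If antibody refusals cannot be logged, narrow secondary objective 1 and its endpoint in Section 8.2 to acceptance of first-line point-of-care RNA testing at recording sites. Counts (b) and (c) must still be kept apart for this to work.

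The cost is a slightly longer aggregate log at sites that keep one; the documents do not show that any site already logs antibody refusals. Under the fallback, the cost is having no acceptance figure for the antibody-first group.
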